6.11.5 Electrocardiograms

Electrocardiograms (ECGs) will be collected during Screening, Month 3, Month 12, and at the end of study in Part A, at the end of study in open-label extension of Part A, and at Screening and the end of the study in Part B. Counts and percentages for ECG diagnosis (normal or abnormal) will also be presented. If the diagnosis was abnormal, counts and percentages for clinical significance will be presented.

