5.2.4 Assessments at Month 3 (\pm 7 days)

At the specified visit, the following procedures will be performed. *Note: Subjects with recurrent disease may, under certain conditions, continue to receive study medications. See Section 7.2.4 for details.*

- Record concomitant medications
- Record adverse events
- Physical examination (including weight, vital signs, and ECOG performance status)

- LDH, CBC, serum chemistry, urinalysis
- ECG (Part A only)
- Biomarker Panel (Part B only)
- Seviprothymut-L or placebo administration

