5.2.5 Assessments at Months 4 and 5 (\pm 7 days)

At the specified visits, the following procedures will be performed, unless the subject has had disease recurrence and terminated study intervention. In that case, the subject will have the procedures outlined in Section 5.2.9 performed, and then enter into a vital status assessment as outlined in Section 5.2.10. Subjects who discontinue study intervention (see Section 6.2.1) but have not progressed should continue to be assessed as described.

- Record concomitant medications
- Record adverse events
- Seviprothymut-L or placebo administration

5.2.6 Assessments at Months 6, 12, 18, 24 (\pm 7 days for Month 6, and \pm 14 days for Month 12, 18, and 24)

At the specified visits, the following procedures will be performed, unless the subject has had disease recurrence and terminated study intervention. In that case, the subject will have the procedures outlined in Section 5.2.9 performed, and then enter into a vital status assessment as outlined in Section 5.2.10. Subjects who discontinue study intervention (see Section 6.2.1) but have not progressed should continue to be assessed as described.

- Record concomitant medications
- Physical examination (including weight, vital signs, and ECOG performance status)
- CBC, serum chemistry, urinalysis
- LDH
- Biomarker Panel (at M6, M12, M18, and M24; Part B only)
- Tumor assessments (see Section 9.3.1)
- Seviprothymut-L or placebo administration
- Record adverse events
- Blood draw for immune monitoring (Part A subjects only)
- Physical examination for autoimmune phenomena (including eye exam by ophthalmologist, and skin exam for vitiligo and rash)
- Autoimmune labs ANA and erythrocyte sedimentation rate (ESR). Other tests (e.g., rheumatoid factor [RF], T4, thyroid-stimulating hormone [TSH]) to be performed only as clinically indicated.
- ECG (Month 12 only, Part A only)

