5.2.8.1 Pre-Recurrence Monitoring Every 3 Months (\pm 7 days)

- LDH (every 3 months)

5.2.8.2 Pre-Recurrence Monitoring Every 6 Months (\pm 7 days for Month 6, and \pm 14 days for every 6 months thereafter)

- Physical examination (including weight, vital signs, and ECOG performance status)
- CBC, serum chemistry, urinalysis
- Tumor assessments (see Section 9.3.1)
- Concomitant Medications

At Months 30 and 36 only (\pm 14 days):

- Blood draw for immune monitoring (Part A subjects only)

At Month 36 only (\pm 14 days):

- Biomarker panel (Part B subjects only)

5.2.9 Assessments to be Conducted at Recurrence (or at Study Completion for Subjects Without Recurrence)

After a subject has had recurrence or the study is completed through the documentation of the pre-specified number of survival events, subjects will report to the clinic within 28 days (\pm 7 days) for a final follow-up (end of study) visit. Assessments are as follows:

- Physical examination (including weight, vital signs and ECOG performance status)
- CBC, serum chemistry, urinalysis
- ECG
- Pregnancy test (urine or blood) for female subjects of childbearing potential
- Blood draw for immune monitoring studies (Part A subjects only), if within 36 months of randomization into study
- Biomarker Panel (Part B only) (see Section 9.3.2)
- Adverse Events (within 30 days of last dose of study drug)
- Concomitant medications

For subjects with tumor assessments that indicate recurrence:

- Confirmation of recurrence through biopsy, if not previously conducted (see Section 9.3)

If survival events have been met, and there is no previous indication of subject disease recurrence:

- LDH (to be followed up by tumor assessments for LDH elevations of 1.5XULN (or greater), provided there are no other obvious medical reasons for the elevated LDH.)

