10.6 Pregnancy and Contraception

All female subjects of childbearing potential will have a pregnancy test (urine or blood) performed at screening and at the post-treatment follow-up visit. Measurement of serum FSH and serum estradiol levels will be performed at screening in female subjects believed to not be of childbearing potential to confirm this status.

Female subjects of childbearing potential must agree to use adequate contraception throughout the treatment duration and for 3 months after the last seviprotilimut-L or placebo dosing. Acceptable contraceptive methods for female subjects of childbearing potential include one of the following:

1. Abstinence
2. One of the following methods:
 - a. Tubal ligation
 - b. Placement of a copper-containing intrauterine device (IUD)
 - c. Condom with spermicidal foam/gel/film/cream/suppository
 - d. Male partner who has had a vasectomy for at least 6 months

- e. Hormonal contraceptives (oral, injected, intrauterine, transdermal, or implanted) provided the subject remains on treatment throughout the entire study and has been using hormonal contraceptives for an adequate period of time to ensure effectiveness (e.g., 3 months).

If a female subject becomes pregnant during the study, treatment will be immediately discontinued and the subject will be removed from study-mandated procedures, except follow-up for survival. The subject will receive counseling from the investigator or designee regarding the nature of the study medication and the potential risk on fetal development.

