Part B1 is a clinical efficacy evaluation (with RFS as the sole primary endpoint) as well as a full safety evaluation compared with placebo in order to assess justification for Part B2. Part B1 has a relaxed type I error probability. A total of 325 subjects will be enrolled into Part B1. Clinical outcome data from Part A and the open-label extension of Part A are not used in the evaluation of clinical outcomes from Parts B1 or B2.

Part B2 is a clinical efficacy evaluation (RFS and Survival) as well as a full safety evaluation compared with placebo and will serve as the pivotal trial. 800 subjects will be randomized into Part B2. Part B2 is designed to standalone and will not use data from Parts A or B1.

Figure 1. Study Flow Diagram

Part A Overview

Overall Study Design:

Doses at W0, W2, W4, W6, W8, M3, M4, M5, M6, then every 3 months through M24**.

[figure not shown]
Key Assessments:

- Safety
- Immunological Response (measured at Week 10)
- Collection of blood samples over 3 years for later analysis of biological activity

* Enrollment in Part A is expected to exceed 99 subjects, as enrollment will continue until the 99th subject completes Week 10.

**At the completion of Part A analysis, subjects receiving 40 or 100 µg POL-103A will continue with the dose to which they have been initially randomized to (i.e., Part A subjects will not cross into Part B). Part A placebo subjects will be removed from the study and may be given the option of enrolling in open-label extension protocol 103A-301OL (Part B dose).

Part B Overview

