¹ At time of recurrence or study completion for subjects without recurrence

² BRAF tumor mutation V600E status must be either known at Screening or a tumor tissue (fresh or archived sample) must be available for testing during the Study.

³ Sera samples and PBMCs will be banked at these time points for biomarker analyses and Immune monitoring (Section 9.3.2 of the Protocol)

⁴ For subjects who have not had recurrent disease

⁵ See Section 9.3.1 of the Protocol for details

⁶ To be performed if the protocol-specified assessments have not been performed after the surgical resection, or the data are not available to the Sponsor

⁷ Include eye exam (by an ophthalmologist) and skin exam for vitiligo and rashes thereafter.

⁸ Adverse events collected through 30 days after last dose.

⁹ New cancer treatments only

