3.6.3 Safety Endpoints

The between-arm comparison of safety endpoints for Part B1 of this study are:

- The incidence of all adverse events (AEs) reported during the study, including the seriousness, severity, and assessed relatedness to study drug
- Number and percent of patients discontinued from study drug treatment due to AEs
- Change from baseline in vital signs, laboratory data, and electrocardiograms (ECGs)

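### The only scheduled Part B follow-up ECG is tied to recurrence or study closure, so the between-arm ECG change endpoint depends on the efficacy outcome

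*SAP*

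**What the plan says.** SAP 3.6.3 lists among the between-arm safety endpoints of Part B1 "Change from baseline in vital signs, laboratory data, and electrocardiograms (ECGs"), and SAP 3.7.2 repeats this for Part B2. SAP 2.1 describes B1 as an RFS evaluation "as well as a full safety evaluation compared with placebo in order to assess justification for Part B2".

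SAP 6.11.5 states when Part B ECGs are taken: "at Screening and the end of the study in Part B". The Part B schedules in both documents agree, with ECG marked in the Screening and End of Study columns only. Protocol 5.2.4 and 5.2.6 restrict the Month 3 and Month 12 ECGs to Part A.

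The End of Study visit is not an end-of-treatment visit. Footnote 1 to the Part B schedule in SAP 2.4 defines it: "At time of recurrence or study completion for subjects without recurrence". Protocol 5.2.9, which lists the ECG, has the patient return "After a subject has had recurrence or the study is completed through the documentation of the pre-specified number of survival events". Protocol 3.1 puts study closure at 432 deaths in Part B2, and SAP 5.2.2 projects that 13 years after the start of accrual. Dosing ends at Month 24 (Protocol 7.2.3).

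The pregnancy test shares the End of Study column with the ECG, while Protocol 10.6 has it "performed at screening and at the post-treatment follow-up visit".

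**The concern.** A change-from-baseline endpoint needs a follow-up value obtained on the same footing in both arms. Here a patient reaches the follow-up ECG by relapsing, or by staying recurrence-free until the study closes. Recurrence is a post-randomization outcome and the primary efficacy endpoint. An ECG comparison at the B1 analysis is therefore a comparison among relapsed patients. If the vaccine works, the arms also differ in the share of patients assessed. No analysis method can recover this, because the missing ECGs are not collected.

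The two routes also measure different things. An ECG at a recurrence during dosing is close to exposure. One taken at closure, years after the last dose, says little about a drug effect. Patients who complete 24 months without recurrence have the fullest exposure, and they have no scheduled ECG near the end of it.

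SAP 6.11.5 adds a smaller gap. It specifies counts of normal, abnormal and clinically significant readings, but no change-from-baseline summary, unlike SAP 6.11.4 for laboratory data and 6.11.6 for vital signs.

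**Working it through.** **Inputs.** B1: 325 patients in 1.5 years, 2:1, 126 RFS events at 3.21 years, power 80.5% (SAP 2.2, 5.2.1). Control RFS rates are 0.154, 0.198 and 0.409 per year, with an empirical stage mix of 30.9, 30.4 and 38.7% (SAP 5.2.1). The hazard ratio is 1 to month 1, falls linearly over 3 months, and is 0.625 from month 4. B2: 800 patients in 3 years, 1:1, 310 RFS events at 3.93 years, 432 deaths at 13 years (SAP 5.2.2).

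**1. Reproducing the plan.** I simulated exponential control times and a vaccine hazard λ2(t) = (λ1 − λ2)g(t) + λ2, with λ2 = 0.625λ1 (SAP Appendix 3), and applied the stratified logrank test at one-sided 0.10. Uniform accrual is my assumption.
- B1, 2,000 replicates: 126th event at a mean of 3.30 years (stated 3.21), power 81.4% (stated 80.5%). Accrual ramps of 0.5 to 1.5 years give 3.42 to 3.55 years.
- B2, 800 replicates, one-sided 0.02: 310th event at 3.94 years (stated 3.93), power 92.9% (stated 90.2%).

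The model is close enough to the plan's own to describe who has had an event.

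**2. Who can have a scheduled follow-up ECG at the RFS analysis.**
- B1: 126/325 = 38.8% at most; the other 325 − 126 = 199 (61.2%) have none scheduled.
- B2: 310/800 = 38.75% at most.

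These are upper limits. Deaths without recurrence count as RFS events but yield no ECG, and patients who continue dosing after an early recurrence are exempt from the 5.2.9 procedures (Protocol 7.2.4).

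**3. Split by arm under the planned effect** (same model).
- B1: about 75 of 217 on vaccine (35%) and 51 of 108 on placebo (47%).
- B2: about 132 of 400 (33%) and 178 of 400 (45%).

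**4. When the B1 recurrence ECGs fall.** About 83% of the B1 events occur within 24 months of entry. Median time to event among those with an event is about 1.05 years in both arms. The visit is due within 28 days (± 7) of recurrence (Protocol 5.2.9).

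**5. Time from the last planned dose to a closure ECG.** Gap = closure − (entry + 2 years).
- B2, first patient: 13 − 0 − 2 = 11 years.
- B2, last patient: 13 − 3 − 2 = 8 years.

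The 13-year projection is taken as stated; the documents give no control survival rates from which to check it. For B1 the gap depends on when B2 accrual starts, which the documents do not fix.

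**6. Whether B1 can still be changed.** B1 accrual was projected to end in June 2016 (SAP 5.2.1), so its last Month 24 visit falls around June 2018. The SAP addendum is dated 24 April 2019, with a 1 January 2019 cutoff. On those dates all B1 patients are past Month 24.

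**The case against.** The strongest reply is that little rests on this endpoint. The protocol's Part B safety endpoint is the incidence and severity of AEs (Protocol 3.5.2, 3.5.3). ECG change appears as an endpoint only in the SAP, as a descriptive table with no test or decision rule. Part A scheduled placebo-controlled ECGs at Months 3 and 12, and 157 subjects were treated there, so lighter ECG monitoring in Part B may be deliberate. In Part B, AEs are collected to 30 days after the last dose, clinically significant ECG abnormalities are recorded as AEs (Protocol 10.7.4), and laboratory tests and vital signs continue through Month 24. This stands. A reader might infer that the B1 safety evaluation as a whole is hollow; the documents do not support that.

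Three other strong readings also fail. A reader might infer that the vaccine arm has fewer ECGs than placebo. With 2:1 allocation it has more in B1 (about 75 against 51), and only the proportion is lower. A reader might take all follow-up ECGs to be remote from dosing, but most of those available at the B1 analysis come during the dosing period. And the pregnancy-test wording in Protocol 10.6 might suggest a missing visit. Protocol 5.2.9 calls its own visit a final follow-up visit and lists the test there, so a loose label is the likelier explanation.

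Protocol 6.2.1 requires a complete final evaluation at withdrawal from study intervention, which might yield some ECGs. Its content is undefined, no ECG is named, and patients who complete dosing are not covered.

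None of this answers the core point: the SAP names a between-arm ECG endpoint that the schedule delivers only according to the efficacy outcome.

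**Conclusion.** The concern holds as a mismatch between a stated endpoint and the schedule meant to supply it. At the B1 analysis at most 39% of patients have a scheduled follow-up ECG, and all of them have relapsed. The arm proportions of about 35% and 47% rest on the SAP's planned effect, its control rates and uniform accrual. With no treatment effect the proportions would be similar, but the comparison would still be confined to relapsed patients. The 8-to-11-year gap applies to B2 patients who stay recurrence-free, and only if B2 opens and runs to 432 deaths; earlier closure shortens it. The 39% does not depend on that.

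The effect is limited to one descriptive safety endpoint. It does not touch RFS, survival or the AE analysis, and nothing in the documents points to an ECG effect in either direction. It should be corrected before B2, because missing end-of-dosing ECGs cannot be collected later.

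**What to change.** Reconcile SAP 3.6.3 and 3.7.2 with SAP 6.11.5, Protocol 5.2.9 and the Part B schedules.

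- For B2, and any patient not yet past Month 24, time the single follow-up ECG used for the endpoint to the end of dosing, at a visit that already exists: Month 24 (Protocol 5.2.6), or the final evaluation under Protocol 6.2.1 for those who stop earlier. State in SAP 6.11.5 that the endpoint is the change from screening to that ECG, and how it will be summarized.
- Keep the End of Study ECG for any patient without an end-of-dosing ECG. This includes B1 patients already past Month 24, who would otherwise have no scheduled post-baseline ECG.
- For B1, report the available ECGs descriptively by arm, with the number and percentage assessed and the time since last dose, and do not present them as an unbiased between-arm comparison.
- Align the visit label for the pregnancy test in Protocol 10.6 with the End of Study visit in 5.2.9 and the schedule.

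The cost is a protocol amendment and a few lines of SAP text. The number of follow-up ECGs per patient stays at one. The late closure ECG is lost for patients who have one at the end of dosing, a small loss since it says little about drug effect. B1 itself cannot be repaired.

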6.11.6 Vital Signs

Vital signs (pulse, temperature, systolic and diastolic blood pressure) and weight will be summarized descriptively for Part A, open-label extension of Part A, and Part B at each scheduled visit and timepoint collected (screening, Visit 1, Month 3, Month 6, Month 9, Month 12, Month 15, Month 18, Month 21, Month 24, and every 6 months thereafter until recurrence or end of study).

Mean and mean change from baseline values will be presented. Change from baseline will be calculated as the post-baseline measurement minus the baseline measurement. If either the baseline or post-baseline value is missing, the observation will not be included in the change from baseline summary.

All vital signs will be presented in data listings by patient and timepoint.

7.0 TABLES, FIGURES, AND DATA LISTINGS

This SAP includes mockups of tables, figures, and data listings (in separate documents) that will be generated.

APPENDIX 1: ACCRUAL RATE

The simulation software used to plan the trial requires specification of the number of subjects to be accrued and the period of time over which accrual is to take place (as is usual with trial planning software). These simple specifications would generate an accrual distribution that is uniform, that is, a constant accrual rate. But since it is unrealistic to assume uniform accrual the software also allows specification of an arbitrary accrual distribution through the specification of intervals and accrual in each interval. An additional feature, and the one used in these computations, allows specification of a linear ramp time for the accrual distribution from which the accrual distribution is generated. The linear ramp time must be less than or equal to the total accrual time. Given the linear ramp time the accrual distribution is generated by assuming zero accrual at time zero and a constant accrual rate increase from time zero through the time specified by the linear ramp time, after which the accrual rate is uniform from the linear ramp time until the end of accrual. The rate of accrual increase during the ramp time and the constant accrual rate after the linear ramp time are derived from the total accrual, the total accrual time, and the linear ramp time. For example, for the computations done in this SAP the following specifications were used: total accrual time of 2 years for 960 patients and with a linear ramp time of 1 year. Figure 1 illustrates accrual rate by month.

Figure 1: Accrual Rate

APPENDIX 2: FUTILITY ANALYSIS METHODOLOGY

The following are the specifications for futility analyses. The futility null hypothesis is $H_0: \Delta \leq HR_A$ where HR_A is the hypothesized specific alternative hazard ratio for the test of the efficacy null hypothesis. The futility alternative hypothesis is $H_A: \Delta > HR_A$. The testing of the futility null hypothesis can be formulated as follows. The futility null hypothesis can be written as

$$H_0: \ln(\Delta) \leq \varphi, \text{ or } H_0: \beta_{\text{arm}} \leq \varphi, \text{ or } H_0: \beta_{\text{arm}} - \varphi \leq 0.$$

where $\varphi = \ln(HR_A)$ and β_{arm} is the “true” logarithm of the hazard ratio associated with the arm variable in the model previously defined. Thus, the test is that $\beta_{\text{arm}} - \varphi$ is zero is a test of the futility null hypothesis. The futility null hypothesis is tested using SAS PHREG using the OFFSET option. When using the OFFSET option the estimated coefficient of the arm variable will be an estimate of $\beta_{\text{arm}} - \varphi$.

If the estimated coefficient of the arm variable is greater than 0 then the associated two-sided P value should be divided by 2 and reported as the one-sided futility P value for assessing whether the futility null hypothesis can be rejected, otherwise the futility null hypothesis is not rejected.

The one-sided futility P value will be compared to the applicable significance level P_F . If the futility P value is less than or equal to P_F then the survival futility boundary will be regarded as having been crossed.

APPENDIX 3: DELAYED EFFECT SIMULATION METHODOLOGY

Following is a description of the simulation methodology used to evaluate the statistical operating characteristics of trials where the intervention under study is subject to a delay of effect. The text that follows is based on a methodological manuscript submitted for publication.

The reasons for a delayed effect include: (1) Randomization of patients with advanced disease for which experimental intervention is “too late”. (2) The experimental intervention has a delayed onset of benefit. One or both of these mechanisms could apply.

Assume a two-arm randomized clinical trial and that individuals entering this trial are to be randomized to one of two groups designated as arms 1 and 2, where arm 1 is to receive control intervention (perhaps a placebo) and arm 2 is to receive experimental intervention. Assume that the outcome of interest is time to a failure event or time to the last date when this event has yet to be observed. Assume it is hypothesized that the experimental intervention induces a distribution of event times that is more favorable, that is, shifted to the right, as compared to the distribution of event times associated with the control intervention. Assume competing events are either nonexistent or negligible. Trials of this type are typically planned by computing the required number of events under the assumption of proportional hazard rates, specific type I and II error probabilities, and a hypothesized clinically consequential ratio of the arm 2 (experimental) hazard rate to the arm 1 (control) hazard rate. Let h_A be the hypothesized consequential hazard ratio.

Let the hazard ratio function $h(t) = \lambda_1(t)/\lambda_2(t)$ where $\lambda_1(t)$ and $\lambda_2(t)$ are hazard rate functions for arm 1 and 2, respectively. The proportional hazard rates assumption means that $h(t) = \lambda_1(t)/\lambda_2(t) = h$ (a constant).

After computing the required number of events, projections for the timing of analyses are usually made based on assuming exponential distributions for the arms with hazard rates $\lambda_1(t) = \lambda_1$ and $\lambda_2(t) = \lambda_2 = h_A \lambda_1$. Thus, when there is no delayed effect the survival functions for arm 1 and arm 2 are usually specified to be

$$F_1(T \leq t) = \exp(-\lambda_1 t)$$

$$F_2(T \leq t) = \exp(-\lambda_2 t) = \exp(-h_A \lambda_1 t).$$

The delayed effect simulation methodology described here is based on assuming that the control arm survival distribution is exponential. It is possible to generalize this methodology to other types of control arm survival distributions.

Now, assume that the experimental intervention has a lag in realization of effect so that the arm 2 hazard rate is initially λ_1 and only later becomes $h_A \lambda_1$. This delay of effect assumes the arm 2 hazard rate function is

$$\lambda_2(t) = (\lambda_1 - \lambda_2)g(t) + \lambda_2, \quad (t \geq 0),$$

where $g(t)$ is a function with the following properties: $g(0) = 1$, $g(t)$ is non-increasing, and either $g(t) = 0$ for some $t' \geq t' > 0$ or $g(t) \rightarrow 0$ as $t \rightarrow \infty$. This implementation of delayed effect specifies that ultimately the hazard ratio becomes proportional or approaches proportionality.

In order to do simulations under delayed effect the survival function $F_2(t)$ must be derived. This survival function is obtained using the relationship

$$F_2(t) = \exp(-H_2(t))$$

where $H_2(t)$ is the integral of $\lambda_2(t)$ from 0 to t (integrated hazard function). Depending on the function $g(t)$ the integral $H_2(t)$ may have an analytic form; if not then numerical integration can be used.

A segmented linear form of $g(t)$ will now be described (other forms of $g(t)$ are possible). The segmented linear form of $g(t)$ has two parameters, d and r , where $d \geq 0$ and $r > 0$. The parameter d is the delay in the start of the effect of the experimental intervention and r is the time it takes to realize full effect from the start of realization of effect. The function $g(t)$ is specified linear and descending between d and $d + r$. Specifically, $g(t)$ is defined as follows

$$\begin{aligned} g(t) &= 1 \text{ for } t < d \\ g(t) &= (d + r - t)/r \text{ for } d \leq t < d + r, \\ g(t) &= 0 \text{ for } t \geq d + r. \end{aligned}$$

It follows that

$$H_2(t) = (\lambda_1 - \lambda_2)t + \lambda_2 t = \lambda_1 t \text{ for } t < d$$

$$H_2(t) = (\lambda_1 - \lambda_2)\{d + [(d + r)(t - d) - (t^2 - d^2)/2]/r\} + \lambda_2 t \text{ for } d \leq t < d + r,$$

$$H_2(t) = (\lambda_1 - \lambda_2)(d + r/2) + \lambda_2 t \text{ for } t \geq d + r.$$

Pseudo random survival times from F_2 can be generated by tabling its inverse and using a uniform pseudo random generator.

Thus, if F_1 is exponential (as usual) and F_2 is defined as above then pseudo random samples of survival times from F_1 and F_2 can be generated for specified values of λ_1 , λ_2 , d and r . These survival times can be converted to clinical trial data based on specification of accrual distribution and follow-up intervals. The net effect of delayed effect is a reduction in projected statistical power relative to no delayed effect. Specifically, events occurring prior to the time of realization of the specified effect h_A will be less differentiating than events that occur after full realization of the specified effect size h_A , and therefore only the events occurring after the time of realization of effect fully contribute to statistical power. Thus, if a trial is planned without taking into account delayed effect then the projected power of the trial will be overestimated if delayed effect is present in the data.

Statistical operating characteristics for a specific set of trial specifications, including parameters specifying a delayed effect, are estimated from replicating the generation trial data for the control arm and the experimental arm, that is, from replicates of the simulated trial data. Thus, for specified significance criteria the statistical operating characteristics of the test of the null hypothesis for superiority of the experimental intervention can be estimated using the logrank test on the simulated trial replicates. The following statistical operating characteristic estimates are most often of interest:

One-sided type 1 error probability: The proportion of replicates for which the test of the null hypothesis is rejected using the one-sided logrank test and when the experimental arm data are generated with $\lambda_2 = \lambda_1$.

- Power: The proportion of replicates for which the test of the null hypothesis is rejected using the one-sided logrank test and when the experimental arm data are generated with $\lambda_2 = h_A \lambda_1$. These estimates also can be made for interim analyses based on event time or calendar time,

and the cumulative estimates (trial-wise) are those that take into whether and when specific trial replicates meet interim analysis criteria.

The statistical operating characteristics of futility tests can also be estimated using simulation. An additional parameter Ω is specified for the generation of experimental arm data replicates so that $\lambda_2 = \Omega\lambda_1$. For futility testing the logrank test is modified with an offset corresponding to h_A so that the futility null hypothesis is for a hazard ratio equal or less than h_A against a hazard ratio larger than h_A . The following estimates are of interest when assessing the statistical operating characteristics of futility tests:

- False futility probability (futility test type I error probability): The proportion of replicates for which the test of the futility null hypothesis is rejected using the futility logrank test and $\Omega = h_A$.
- Probability of futility conditional on Ω : The proportion of replicates for which the test of the futility null hypothesis is rejected using the futility logrank test and $\Omega \neq h_A$, usually $\Omega > h_A$.

When delayed effect is specified the false futility probability cannot be regarded as the test size because the logrank test when $\Omega = h_A$ will be based on data that inherently violates proportional hazards. When delayed effect is specified and $\Omega = 1$ then the estimate of the probability of futility can be regarded as unbiased because in fact there will be no delayed effect. However, when delayed effect is specified and $\Omega \neq 1$ then the accuracy of the estimated probability of futility will depend on how closely the parameters specifying the delayed effect in the simulations correspond to the actual delayed effect applicable at the time of the futility test. Therefore, when assessing the statistical operating characteristics of a trial with a conjectured delayed effect it is important to generate statistical operating characteristics for a range of possibilities.

ADDENDUM #1

to STATISTICAL ANALYSIS PLAN

Final v4.0

A Multicenter, Double-blind, Placebo-controlled, Adaptive Phase 3 Trial of POL-103A Polyvalent Melanoma Vaccine in Post-resection Melanoma Patients with a High Risk of Recurrence

Study Drug: Seviprotimut-L (formerly POL-103A)

Protocol POL103A-301

Polynoma LLC
[name]
[name]
[name]

Date of Plan: Version 1 September 11, 2012
 Version 2 December 2, 2013
 Version 3 July 25, 2014
 Version 4 August 5, 2016

ADDENDUM #1

to STATISTICAL ANALYSIS PLAN

Final v4.0

